Objectives	
The study will contain two distinct pathways, Study A and Study B, in order to efficiently execute the protocol. Study A will focus primarily on measurements obtained as part of routine clinical care. Study B will focus on enhanced imaging and physiology techniques in patients using lingual muscle stimulation (Inspire).
 
*As of 6/11/2021, the target recruitment for Study A was completed*
 
Study A:
 
 • To determine the contribution of defects in upper airway function to the pathogenesis of airway obstruction at specific sites of pharyngeal collapse by characterizing upper airway pressure-flow/area relationships during DISE. • To determine the impact of jaw thrust and mouth closure maneuvers to functional determinants of upper airway obstruction at specific sites of pharyngeal collapse. • To examine effects of maxillo-mandibular restriction and tongue size on upper airway functional properties during DISE. 
Study B (In addition to the objectives for Study A):
 
 • To assess effects of stimulating specific lingual muscles on upper airway patency during natural sleep and drug-induced sleep • To assess whether craniofacial morphology predicts improvements in pharyngeal patency during sleep with stimulation.

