Patients with implanted hypoglossal nerve stimulation (Inspire[®]) devices will be recruited for this protocol from the University of Pennsylvania or Thomas Jefferson University. All study procedures will be conducted by the clinical research team at the Hospital of the University of Pennsylvania campus (including HUP main, HUP Pavilion and PCAM). Medical records of these referrals will be assessed preemptively or at the time of the clinic or procedure visit for eligibility for this protocol. The patients will be asked whether they are interested in participating in the protocol, at which point informed consent will be obtained for those willing and eligible to enroll. Participants will also

complete a standard MRI screening form to assess eligibility for MRI, including potential claustrophobia.

Design (see Study Flow below)

Participants will initially be consented and screened for this study with a brief medical history and physical exam ([Visit #1](#)). The diagnosis of obstructive sleep apnea may be confirmed from prior sleep study reports. This visit may occur during routine clinical follow-up, if applicable, and may have already been completed prior to study enrollment (primary exception: Thomas Jefferson University patients). Once all inclusion criteria have been met, participants will continue with 3 additional assessments/visits (total 4 visits) per research protocol. In order to facilitate scheduling, these visits may occur in any order:

Eligible participants will undergo upper airway imaging ([Visit #2](#)), where craniofacial morphology will be assessed with MRI measurements and digital morphometric measurements (Study B only).

Participants will then attend an in-lab overnight sleep study ([Visit #3](#)). This will be a full standard polysomnography study where brain activity, body movements, modified EKG, respiratory parameters, and oxygenation will be monitored according to gold standard AASM guidelines. The sleep study will be performed in a split-night fashion including (1) a baseline sleep assessment to measure apnea severity, and (2) hypoglossal nerve stimulation with Inspire to measure response to therapy.

[figure not shown]

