Prior to sleep, patients will undergo facial measurements. A digital camera with laser pointers will be used to capture a series of craniofacial photographs (frontal, profile and neck extended) and intra-oral photographs (junction of the hard and soft palate, airway, or base of tongue). The participant will then perform serial tongue force exercises using a bulb behind their front teeth to assess tongue force.

Thereafter, responses to stimulation will be assessed during DISE with ultrasound measurements of tongue morphology and with measurements of pharyngeal patency during DISE ([Visit #4](#)). Responses in pharyngeal patency will be assessed with video endoscopy, pharyngeal manometry, and tidal airflow monitoring (Studies A+B) while briefly stimulating tongue muscles during DISE (Study B only).

COVID-testing for each of the visits/assessments listed above will be required per departmental guidelines/regulations.

Each of the specific study procedures shown in the Study Design are described immediately below.

Study Flow Diagram

Abbreviations:

- OSA: Obstructive Sleep Apnea
- DISE: Drug-Induced Sleep Endoscopy
- Hx/PE: History/Physical Exam
- HGNS: Hypoglossal Nerve Stimulation

ASSESSMENT #1: CRANIOFACIAL
MRI SCAN (Visit #2)
 • Bony morphology
 • Tongue Size
 • Fat content
 • Pharyngeal lumen size

+

ASSESSMENT #2: OVERNIGHT
SLEEP STUDY (Visit #3)
SPLIT PSG: $\frac{1}{2}$ baseline, $\frac{1}{2}$ HGNS (settings unchanged from clinical optimization)

+

ASSESSMENT #3: DISE STUDY
(Visit #4)
 • Pharyngeal Videoendoscopy
 • Tidal Airflow and CPAP changes
 • Pharyngeal Manometry
 • Submental Ultrasound

	Visit 1: Screening/ Consent*	Visit 2: MRI	Visit 3: Sleep Study*	Visit 4: DISE
Informed Consent	X			
History and Physical	X			
Questionnaires	X			

**Study A (Baseline
Protocol)**

DISE				X
Pharyngeal Manometry				X
Tidal Airflow Monitoring				X
Airflow Manipulation				X
Ultrasound				X

**Study B (Stimulation
Protocol)**

MRI		X		
Digital Morphometrics			X	
Tongue Force			X	
In-Lab Sleep Study			X	
DISE				X

Pharyngeal Manometry				X
Tidal Airflow Monitoring				X
Airflow Manipulation				X
Ultrasound				X
Nerve Stimulation			X	X

*The screening/consent visit may occur during the first scheduled assessment (MRI, PSG, or DISE) to facilitate scheduling and reduce patient burden.

Visit #1: Clinical Evaluation

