1. **Baseline Questionnaires:** Standard screening questionnaires will be administered initially at the time subjects are screened and consented. These questionnaires will assess several demographic, anthropometric, and physical health domains (see attached questionnaires). We will administer the standard Sleep Surgery clinical questionnaire which includes ESS, ISI, FOSQ-10, NOSE, sleep quality, snoring, etc. We will perform an Inspire device download to evaluate study eligibility (therapy compliance), and record their treatment settings. Patients without the most recent Inspire remote will be provided with one.

Visit #2: Overnight Sleep Study, Digital Morphometrics, Tongue Force Assessment

1. **Sleep study monitoring (polysomnography):** Standard monitoring of sleep will occur during Visit #2. For patients opting for Study A only, the sleep study may have already been performed as part of routine clinical care. For Study B, overnight nocturnal recordings will be performed in our sleep laboratory and will follow the same procedures (#1-5) outlined in Visits #3-4 below. The study will include monitoring of EEG, submental EMG, EOG, S_pO_2 , tidal airflow, thoraco-abdominal efforts, and body position. Recordings will be archived on an institutionally secured and managed network drive and accessible only to study personnel. Recordings will be accessed via a HIPAA secured web portal. Patients will be required to wash out from therapy between 5-7 days prior to PSG, i.e. they cannot use HGNS or other therapies during this time. A split night study will be performed (partially with HGNS, partially without). HGNS will not be titrated, i.e. we will use the settings optimized by clinical care prior to study participation. Patients must have a minimum of one hour of supine non-REM stage 2 sleep during both the baseline and treatment (with HGNS) assessments. If patients are unable to meet these criteria, they will not proceed with DISE.

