Participants will temporarily stop all therapy for OSA (particularly Inspire) for 5-7 nights prior to their sleep study. Each participant's medical therapy will continue unaffected by this study with the addition of submental ultrasound examination, MRI, and of one unscheduled polysomnography.

5. Inclusion/Exclusion Criteria

Inclusion Criteria:

- Adult patients (≥ 22 yrs) willing and capable of providing informed consent
- Implanted with the MRI-conditional Inspire hypoglossal nerve stimulator (Model 3028)*
- Compliant with Inspire therapy (> 20 hours/week over 2+ weeks) as a standalone treatment for sleep-disordered breathing
- Inspire Remote Model 2500 or later

Exclusion Criteria:

- MRI contraindications (claustrophobia, ferromagnetic implants/foreign bodies, etc.)*
- Inspire Model 3024
- Inspire Remote Model 3032
- Patients who have fallen asleep while during resulting in an accident or “near miss” accident within 1 year prior to device implantation.
- Inability to sleep in the supine position (by self report)
- History of severe difficulty initiating or maintaining sleep in the laboratory.
- Pregnant women**

* The Inspire model 3028 is not considered an MRI contraindication.

**Women of child bearing potential must undergo a urine pregnancy test (UPT) prior to enrollment. A second UPT is performed prior to DISE as part of routine clinical workup. This study involves temporarily stopping treatment of obstructive sleep apnea, which may harm the fetus.

6. Drugs/Substances/Devices

a. The rationale for choosing the drug and dose or for choosing the device to be used.

We will administer propofol, which is routinely given for DISE procedures. The rationale for choosing this drug is based on its reliability, well-established tolerability, safety, and low muscle-relaxant profile.

Lidocaine jelly (~ 2 mL) will be squirted into each nostril prior to passing the pharyngeal catheter and endoscope.

The protocol will involve recruiting patients already implanted with the Inspire HGNS system. We have selected this device in place of stimulating with custom fine-wire electrodes to reduce patient burden. The Inspire device is safe, well-tolerated, and FDA-approved for treatment for OSA.

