Using an ANOVA framework for estimating sample size for a 1x3 factorial design (Specific Aim A: complete responder, partial responder, and non-responder), we calculate the sample required to detect within-subject changes in upper airway function (e.g., the severity of upper airway obstruction during DISE as reflected by measurements of pharyngeal collapsibility, P_{CRIT}), based on published data demonstrating decreases in pharyngeal collapsibility (P_{CRIT}) of $\sim 3.5 \pm 2.0$ cmH₂O during stimulation ³⁴. This response accounts for $\sim 24\%$ of the total variance (η^2), which yields an effect size (f) of ~ 0.40 . Our data also demonstrate within-subject correlations of at least 0.5 for repeated P_{CRIT} measurements ^{69,70}. Using these parameters, we calculated that 15 subjects would be required to detect significant differences in each of 3 responder categories with an alpha of 0.05 and a power of 90%. To account for measurements in both sexes, subject attrition, and incomplete measurements, we propose an 'n' of 45 subjects to complete the protocol. We also plan to examine the effects of sex and BMI on this outcome, which will require an additional 30-60 subjects (total n = 100) for the entire protocol. This sample size will allow us sufficient power to detect substantial effects of stimulation on tongue morphology (Specific Aim B) and effects of craniofacial structures on tidal airflow and markers of airway collapsibility (Specific Aim C).

d. Early stopping rules.

- This is a low-risk study designed to examine underlying mechanisms of action of lingual and hypoglossal nerve stimulation treatment in patients with obstructive sleep apnea. Since the protocol will involve temporarily stopping HGNS treatment for 5 days, one risk includes excessive daytime sleepiness. We have attempted to minimize subject risk with the strict exclusion criterion, "Patients who have fallen asleep while during resulting in an accident or 'near miss' accident within 1 year prior to device implantation." In addition, we will advise patients against driving and operating heavy machinery during this 5-7 night washout period and we will perform a check-in call after the first 2 nights without therapy. We will specifically ask patients if they have fallen asleep while driving, and will withdraw any patients answering yes. We also recognize and inform each subject of his/her right to withdraw from the clinical study at any time.

8. Risks

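### Study B lets DISE be booked before the sleep study, yet entry to DISE depends on sleep minimums that only the sleep study can show

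*SAP*

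**What the plan says.** The rule on sleep is in Section 4a, under Visit #2 (sleep study monitoring): "Patients must have a minimum of one hour of supine non-REM stage 2 sleep during both the baseline and treatment (with HGNS) assessments". Its consequence follows at once: "If patients are unable to meet these criteria, they will not proceed with DISE".

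The rule on order is earlier in Section 4a, in the Design text that introduces the three assessments after screening: "In order to facilitate scheduling, these visits may occur in any order". DISE is one of the three. The footnote to the visit table adds: "The screening/consent visit may occur during the first scheduled assessment (MRI, PSG, or DISE) to facilitate scheduling and reduce patient burden".

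Three other places bear on how these are read:

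- The Study Summary records, "As of 6/11/2021, the target recruitment for Study A was completed", so the current text mainly governs Study B.
- Under Visit #2, only Study A patients may rely on a sleep study already done in routine care. Study B patients have a new in-laboratory split night after a washout of 5 to 7 days.
- Section 5 screens ability to sleep supine by self-report and ability to sleep in the laboratory by history.

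**The concern.** A gate on DISE that is read from the PSG presupposes that the PSG has been done. The any-order rule removes that guarantee, and nothing in the document exempts DISE from it. Section 5 offers no substitute, because neither criterion measures the required hour in each part of the night.

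Two consequences follow. First, two patients with the same inadequate PSG are treated differently: the one booked for PSG first is stopped, and the one booked for DISE first is sedated with propofol and measured. Pharyngeal area, one of the primary outcomes in Section 7a, is measured at DISE, and airflow is recorded there too. Membership of that data set would therefore depend partly on scheduling. Second, the plan does not say whether DISE data stay in the analysis when a later PSG misses the minimums.

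There may be a third consequence. The sample size in Section 7c rests on three responder categories that the plan does not define. If they come from the split night, whose second part is "hypoglossal nerve stimulation with Inspire to measure response to therapy", a DISE-first patient who misses the minimums would have DISE data but no category based on the required sleep time. That link is an assumption.

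**Working it through.** The plan has no figure of its own to reproduce. The check compares the rules and then bounds the size under stated assumptions.

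**Which orders defeat the gate.** MRI, PSG and DISE can be arranged in 3! = 6 ways, all permitted by the Design text.

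- PSG before DISE, gate works: MRI–PSG–DISE, PSG–MRI–DISE, PSG–DISE–MRI.
- DISE before PSG, gate cannot work: DISE–MRI–PSG, DISE–PSG–MRI, MRI–DISE–PSG.

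So three of six orders defeat it, and in two of those DISE is the first assessment.

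**Inputs for size.**

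- N = 100 for Study B (Study Summary), or 45, the number Section 7c proposes to complete the protocol before it adds subjects for sex and BMI.
- d = share of patients having DISE before PSG. Not in the plan; assumed 10%, 25% or 50%. The 50% corresponds to all six orders being used equally.
- q = share missing the sleep minimums after any repeat PSG. Not in the plan; assumed 5%, 10% or 20%. The upper value borrows the 20% in Section 4b for patients not completing all visits, which has other causes as well.
- Difference in on–off response between patients who would fail the gate and the rest: assumed 1.0 cmH2O smaller. The plan's reference response in Section 7c is 3.5 ± 2.0 cmH2O.

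**Formulas.**

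- Patients reaching DISE although the gate would exclude them = N·d·q.
- Patients in the DISE analysis = N·[1 − (1 − d)·q], because only PSG-first failures are removed.
- Share of the analysis = d·q / [1 − (1 − d)·q].
- Shift in mean response = share × 1.0 cmH2O.

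| d | q | N = 100 | N = 45 | Share of DISE analysis | Shift, cmH2O | Shift as % of 3.5 |
|---|---|---|---|---|---|---|
| 0.10 | 0.05 | 0.5 | 0.2 | 0.005/0.955 = 0.5% | 0.005 | 0.15% |
| 0.25 | 0.10 | 2.5 | 1.1 | 0.025/0.925 = 2.7% | 0.027 | 0.77% |
| 0.50 | 0.20 | 10 | 4.5 | 0.100/0.900 = 11.1% | 0.111 | 3.2% |

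With PSG always first, d = 0 and every entry is 0.

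**Scale.** Reading the ± 2.0 as a standard deviation, the standard error of the mean response is 2.0/√100 = 0.20 at n = 100 and 2.0/√45 = 0.30 at n = 45. The largest shift in the table, 0.11, is below both.

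**The case against.** The best defence is that the specific rule governs the general one. The gate's wording presupposes a completed PSG, and the any-order sentence is only a scheduling convenience. Every listing in the document puts DISE last. The visit numbers in the Design text and in the detailed procedures differ only by exchanging MRI and PSG, and Section 10 numbers DISE as the last assessment. That is probably what the sponsor intends. But the document never says that PSG must precede DISE, and the sentence introducing the sequence says the opposite. Staff who book from the Design text would comply with it and still defeat the gate.

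The footnote is weaker evidence than the Design text. It concerns when consent may be taken, and its list could pool the two studies, with DISE listed for Study A. That reading is possible. The footnote does cover Study B, since MRI and the in-laboratory sleep study appear in the table only there, but the conflict stands on the Design text alone.

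The sedation harm is also arguable. Section 4a describes the sedation and endoscopy steps as standard of care, and Section 4d does not list DISE among the additions to usual treatment. Against that, the Design text counts DISE among the visits required by the research protocol. It is safer to say that these patients undergo a DISE the plan says they should not have than to say that each receives a wholly extra sedation.

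Finally, the size rests on assumptions throughout. Nothing in the document links missing the sleep minimums to a smaller response under propofol. Section 10 also provides payment for a repeat PSG, which would lower the failure rate. These points limit the weight of the finding and leave the contradiction in place.

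**Conclusion.** The concern holds and is minor. The any-order rule and the gate on DISE cannot both be followed in three of the six permitted orders, and no text reconciles them. This part needs no assumption.

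The effect on results is probably small. Each patient's on–off contrast is made within one session, so a wrongly included patient still gives a valid comparison. What changes is who is in the analysis. The ranges above show what plausible values would imply; they are not estimates, because the plan supplies neither d nor q. The main practical cost is that entry to DISE, and to its data, can follow booking order in place of the plan's own criterion.

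**What to change.** For Study B, amend the Design text in Section 4a so that MRI may take place at any point but the PSG, with its sleep minimums met, must precede DISE. Limit the table footnote so that only MRI or PSG can be the first assessment in Study B.

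If any Study B patient has already had DISE first and then missed the minimums, state whether those data are kept, and report the main DISE result with and without them.

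The cost is two sentences of text and some scheduling freedom, since DISE can no longer be booked ahead of the PSG. No procedure is added, and neither is any time off therapy.

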a. Medical risks, listing all procedures, their major and minor risks and expected frequency.

Baseline Questionnaires: These surveys acquire information that is routinely collected in the process of enrolling participants in clinical studies. There are not any significant physical risks with these procedures. As with all medical information, there is always the risk of psychological distress if personal health information is not held confidential. In order to minimize this risk, electronic PHI will be stored in a password-protected database (REDCap), and written information will be stored in locked files or file-rooms when not attended by study personnel.

Therapy Washout: Patients participating in Part B will undergo a 5-7-night therapy washout, i.e. they will not use Inspire for treatment of obstructive sleep apnea during this period. Untreated OSA increases the risk for excessive daytime sleepiness and consequently, motor-vehicle accidents. We have attempted to minimize subject risk with the strict exclusion criterion, "Patients who have fallen asleep while driving resulting in an accident or 'near miss' accident within 1 year prior to device implantation." In addition, during the patient consent (Visit 1), we will advise the patient against driving while sleepy. We will also perform a check-in call after 2 nights off therapy.

Ultrasound procedure for tongue imaging: Ultrasound is a non-invasive, inexpensive, and easy way to examine the morphology of the tongue and its response to stimulation. There is minimal discomfort associated with examination.

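### The drowsy-driving exclusion stops at implantation, so a later sleep-related crash or near miss does not keep a patient out of the 5-7 night washout

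*SAP*

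**What the plan says.** The criterion appears four times in the SAP: in the Study Summary, in section 5, in section 7d (Early stopping rules) and in section 8a (Medical risks, Therapy Washout). Each time the look-back is the same: an "accident within 1 year prior to device implantation". Sections 7d and 8a both offer it as protection for the washout: "We have attempted to minimize subject risk with the strict exclusion criterion".

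The plan adds other measures:

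- Section 7d, on driving: "we will advise patients against driving and operating heavy machinery during this 5-7 night washout period".
- Section 7d also schedules a telephone contact early in the washout: "we will perform a check-in call after the first 2 nights without therapy".
- Section 7d, next sentence: "We will specifically ask patients if they have fallen asleep while driving, and will withdraw any patients answering yes".
- Section 8a gives narrower advice, at consent: "we will advise the patient against driving while sleepy". It repeats the call after 2 nights.
- Visit #1 (section 4a) includes a medical history and questionnaires: "We will administer the standard Sleep Surgery clinical questionnaire which includes ESS, ISI, FOSQ-10" and others.

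The footnote to the visit schedule in section 4a states: "The screening/consent visit may occur during the first scheduled assessment (MRI, PSG, or DISE").

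**The concern.** Section 8a itself says that untreated sleep apnea raises the risk of daytime sleepiness and hence of motor-vehicle accidents. The washout recreates that state for research purposes, and section 9 expects no direct benefit to participants. An entry criterion meant to limit this risk should take account of the patient's most recent driving history. This one stops at implantation, which for some participants may be years before they enrol. Someone with recent evidence of sleepy driving can then be taken off therapy with no entry rule against it. The possible harm is a road crash, which endangers others as well as the participant.

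**Working it through.** No sample-size or test calculation is involved. The check sets the criterion's time window against the enrolment sequence, and then asks whether another provision fills the gap.

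**1. The window.** The criterion covers the 12 months that end at implantation. Sections 4a and 5 require the device to be implanted already, with more than 20 hours of use per week over at least 2 weeks. Section 5 sets no maximum time since implantation. The uncovered period runs from implantation to enrolment: at least those 2 weeks, with no upper bound. For anyone implanted 1 year or more before enrolment, the whole of the most recent year is uncovered.

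Example: implantation 24 months before enrolment. The covered period runs from 24 + 12 = 36 months to 24 months before enrolment. A near miss 1 month before enrolment falls outside it.

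**2. Other exclusions in section 5.** These concern MRI contraindications, device and remote models, inability to sleep supine, severe difficulty sleeping in the laboratory, and pregnancy. None addresses driving or sleepiness after implantation.

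**3. Is the uncovered time safely treated time?** Not necessarily.

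- The compliance threshold is 20 / 7 = 2.86, or about 2.9 hours per night. It measures use, not response.
- Section 7c plans for complete, partial and non-responders.
- Section 9 accepts that some device users may be treated suboptimally.

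**4. The other measures.**

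- *Driving advice* (7d, 8a) is advice. The two sections differ: no driving during the washout in one, no driving while sleepy in the other.
- *The driving question* (7d) sits under early stopping rules, directly after the check-in call, and leads to withdrawal. No look-back is stated. There are two readings:
  - Asked at the call, with no look-back: it can catch a post-implant event, but 2 nights have passed. As a share of the washout, 2 / 7 = 0.29 and 2 / 5 = 0.40.
  - Asked about the washout only: an earlier post-implant event is missed, and the patient can complete all 5-7 nights.
- *History, ESS and FOSQ-10* (Visit #1) are collected, but no eligibility criterion uses them.

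**5. Timing of Visit 1.** The schedule footnote lets screening and consent coincide with the sleep study. The washout comes before the sleep study, so a question asked only at Visit 1 could come after therapy has already been stopped.

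**The case against.** The pre-implant year is a sensible choice. It is the patient's untreated period, and the washout returns the patient to that state. The wording is identical in all four places, so it looks deliberate. This stands, and it makes the criterion incomplete rather than misdirected. It would close the gap only if time since implantation were reliably well treated, which the plan does not assume.

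The section 7d question is broader than the criterion. It needs no crash or near miss and states no look-back, so on its plain wording the example patient would answer yes and be withdrawn. The text also does not say that it is asked only at the call. Both points are fair. But the question is placed as a stopping rule after the call, and its consequence is withdrawal. Nothing requires it to be asked before therapy stops.

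All participants receive driving advice, and the investigator sees the Visit 1 history. These measures reduce the risk, but they leave entry to discretion.

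A window reaching back without limit to implantation is asymmetric: a near miss four years ago but after implantation would exclude, while one 13 months before implantation would not. That is true. A window of one year before enrolment would answer the concern about recent events, but added to the existing window it would leave an uncovered stretch for anyone implanted more than a year earlier. The continuous window is simpler.

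Finally, the point does not touch the estimand, power or analysis. That is correct. It is a participant-safety point.

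**Conclusion.** The gap is real and is the same in every statement of the criterion. As written, the plan admits a patient with a sleep-related crash or near miss between implantation and enrolment to the 5-7 night washout. The conclusion about entry rests on the text alone. The consequence after entry depends on how the section 7d question is read: exposure is 2 nights if it has no look-back and is asked at the call, and up to the full 5-7 nights if it covers only the washout. If staff ask it before therapy stops, such a patient could be caught in time, but the plan does not require this. The documents do not give the number of patients affected, and no crash risk can be derived from them. Because partial safeguards exist and the remedy is cheap, this should be fixed, but it does not threaten the study's results.

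**What to change.** - In the Study Summary and sections 5, 7d and 8a, extend the exclusion to events in the year before implantation *or at any time since implantation*. The window is then continuous up to enrolment.
- Ask the existing driving question at Visit 1 and again before the washout starts, as well as at the check-in call. The pre-washout question is needed because Visit 1 may coincide with the sleep study.

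The cost is one line of criterion wording in an amendment and an existing question asked at two earlier points. A few otherwise eligible patients may be excluded.
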